In addition, because there is no standardized clinical assay for anti-fXa activity, it is not possible to use anti-fXa activity as a marker of anticoagulation for purposes of enrollment into the study. However, samples for anti-fXa activity (as well as for anticoagulant plasma free fraction and thrombin generation) are being collected for later analysis at a central laboratory. As a surrogate for elevated anti-fXa activity, the eligibility criteria restrict enrollment to patients who received their last dose of FXa inhibitor within 18 hours if the timing is known. (If the timing of the last dose of FXa inhibitor is unknown, the and exanet bolus must begin as soon as possible—following signing of the ICF and completion of pre-treatment procedures—but no later than 3 hours following signing of the ICF.) The 18-hour time point was selected to enroll the maximum number of patients while avoiding enrolling a large number of patients who are non-evaluable for the primary efficacy analysis due to low anti-fXa activity levels. The 18-hour time point is the approximate time, following a dose of rivaroxaban, to a plasma concentration that is approximately equal to twice the mean trough level at 24 hours. From Study 12-502, it was empirically determined that, at these concentrations, anti-fXa activity is still elevated and thrombin generation is still suppressed. Therefore, it is likely that there is an increased risk of bleeding within this 18-hour window, which is likely the result of FXa inhibition or aggravated by FXa inhibition.

Only patients who are determined to have effective levels of anticoagulation will be considered evaluable for efficacy purposes. For apixaban and rivaroxaban, an anti-fXa activity level of ≥ 75 ng/mL (as determined by central laboratory evaluation) was selected. This level corresponds to anti-fXa activity achieved at twice the mean plasma rivaroxaban concentration at 24 hours after administration of the highest approved doses of anticoagulant (mean 44 ng/mL, 5th and 95th percentile range, 12-137 ng/mL) [14]. Similarly, for apixaban, 75 ng/mL represents the anti-fXa level achieved at twice the mean plasma apixaban concentration at 12 hours following a 5 mg dose based on data from the 12-502 study. These converging data form the basis of the selected anticoagulant last dose window and cutoff for anti-fXa level.

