11.6. Determination of Sample Size

The initial sample size is based on the second primary efficacy variable. A sample size of 162 efficacy evaluable patients will provide 80% power for a two-sided 95% CI that is completely above 50% for the second primary efficacy variable of effective hemostasis, demonstrating a response rate above 50% for that variable. This is based on an anticipated response rate of 61%. Further details on the sample size calculation are provided in the SAP.

The power to demonstrate a decrease in anti-fXa activity is expected to be higher than that to demonstrate a change in hemostatic efficacy. In prior studies in healthy normal subjects, the mean percent change in anti-fXa activity was -93.9 with a standard deviation of 1.7 within 5 minutes of the end of the administration of a bolus of andexanet, compared to -20.7 (8.6) within 5 minutes of the end of the administration of a bolus of placebo, among subjects who had received apixaban dosed to steady state. With 162 patients in the Efficacy Analysis Population with baseline anti-fXa activity of at least 75 ng/mL for patients receiving apixaban and rivaroxaban, 40 ng/mL for patients receiving edoxaban, and 0.25 IU/mL for patients receiving enoxaparin, the power to demonstrate that the true percent change is less than 0 is over 99%.

It is estimated that approximately 30% of the andexanet-treated patients will have pre-andexanet anti-fXa activity of < 75 ng/mL for patients receiving apixaban and rivaroxaban, < 40 ng/mL for patients receiving edoxaban, and 0.25 IU/mL for patients receiving enoxaparin, and therefore these patients will not be included in the primary analysis. Additionally, it is estimated that up to 5% of patients will be unevaluable for reasons unrelated to andexanet. In addition, enrollment will continue until at least 110 evaluable ICH patients (50 of whom are deemed to be high risk) are enrolled to more comprehensively capture clinical outcomes in this high risk patient population. Therefore, it is anticipated that up to 250 patients may have to be treated to achieve the requisite number of evaluable patients.

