5.2. Analysis Populations

5.2.1. Safety Population

The Safety Population will consist of all patients treated with any amount of andexanet.

5.2.2. Efficacy Population

The Efficacy Population will include all patients in the Safety Population who meet all of the following criteria:

- Are determined by the EAC to meet the clinical bleeding inclusion criteria.
- Have a baseline anti-fXa level
- Baseline anti-fXa level of at least 75 ng/mL for apixaban and rivaroxaban, 40 ng/mL for edoxaban, and 0.25 IU/mL for patients receiving enoxaparin.

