For the DOACs, current guidelines by the subcommittee on control of anticoagulation of the International Society on Thrombosis and Hemostasis (ISTH) and the French Working group on perioperative hemostasis (GIHP) recommend using a value of 30 ng/mL to determine if antidote administration should be considered.[4, 5] Unfortunately there is no similar threshold for the indirect anticoagulants, therefore the threshold for the Enoxaparin patients in the analysis will be the lower limit of detection (0.10 IU/mL). Sensitivity analyses excluding patients taking Enoxaparin will be performed as well, with (1) the log of anti-fXa at on-treatment Nadir as a covariate, and (2) the dichotomous variable for anti-fXa less than the threshold as a covariate.

A summary of the planned analyses is below:

Model	Population	Reduced Model covariates	Full Model covariates
1	Efficacy, excluding patients with Non-Evaluable Hemostatic Efficacy due to Admin reason	None (intercept only model)	Indicator variable for on- treatment Nadir anti-fXa level < threshold*
2	Same as (1) except exclude Enoxaparin patients also	None (intercept only model)	Indicator variable for on- treatment Nadir anti-fXa level < threshold*
3	Same as (1) except exclude Enoxaparin patients also	None (intercept only model)	Log of on-treatment Nadir anti-fXa level

4	Same as (1) except exclude non-ICH patients also	Log of (baseline ICH volume +1), Indicator	Reduced Model covariates plus Indicator variable for
	non-reri patients also	variable for Infratentorial	on- treatment Nadir anti-
		involvement	fXa level < threshold*

^{*}The threshold=30 ng/mL for Apixaban, Rivaroxaban and Edoxaban, and 0.10 IU/mL for Enoxaparin.

Descriptive statistics, odds ratios with the corresponding 95% confidence intervals, and p-values from the models will be presented. The Full Model will be compared to the Reduced Model with a Likelihood Ratio Test. The Reduced Model will be rejected in favor of the Full Model if the Likelihood Ratio Test p-value is <0.05.

The area under the receiver operating characteristic (AUC under ROC) with the 95% CI will be presented.

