All deaths will be assessed, and the causes of death adjudicated, by the EAC. Deaths due to cardiovascular causes (i.e., resulting from MI, sudden cardiac death, heart failure, stroke, CV procedures, CV hemorrhage, and other CV causes) will be classified as related to bleeding or non-hemorrhagic.

Kaplan-Meier curve for time to death will be presented by treatment by FXa inhibitor, and exanet dose, and and exanet manufacturing process. Patients who discontinue the study prior to Day 30 with an unknown survival assessment will be censored at the time of the last visit. Also, patients that completed the study (i.e., Day 30) will be censored at Day 30.

In addition, the proportion of patients that died during the 30 day follow-up with exact 95% CI will be presented for the overall safety population, by age category, region, FXa inhibitor, bleeding type, and exanet dose, and exanet manufacturing process, and by age deciles. In addition, the cause of death will be summarized.

The relationship between anti-fXa and 30-day mortality, will be analyzed (in the safety population), using a logistic regression model, with Age included as a covariate.

- 30-day mortality will define Death as Death at any time (including deaths recorded after Day 30). A sensitivity analysis defining Death as above (died during the 30 day followup) will be performed as well.
- Age will be entered into the model using a cubic spline transformation to best reflect the relationship with mortality.

- The Full Model will be compared to the Reduced Model with a Likelihood Ratio Test. The Reduced Model will be rejected in favor of the Full Model if the Likelihood Ratio Test p-value is <0.05.
 - Reduced Model: includes Age (with cubic spline transformation)
 - Full Model: includes Age (with cubic spline transformation) and an indicator variable for anti-fXa at on-treatment Nadir < threshold (where the threshold is 30 ng/mL for the DOACs, and 0.10 IU/mL for Enoxaparin).
- The area under the receiver operating characteristic (AUC under ROC) with the 95% CI will be presented for the Full Model.
- Descriptive statistics, odds ratios with the corresponding 95% confidence intervals, and p-values from the models will be presented also.

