5.17.2. Changes to the Analysis Plan

This analysis plan is an update to version 3.0 (09 August 2019). The main changes to version 3.0 of the Statistical Analysis Plan are:

- 1) Remove stratification of Generation 1 and 2 from all analyses
- Include an extra definition and summary of Thrombotic Events using a broader list of preferred terms, per FDA request
- 3) Reclassify Urinary Bleeds from the "GI" category to the "Other" category
- 4) Pre-specify an analysis of the
 - a. correlation between reversal of anti-fXa activity with effective hemostasis, and
 - b. correlation between reversal of anti-fXa activity with mortality

Previous Changes to SAP

The previous analysis plan was an update to versions 1.0 (30 October 2018) and 2.0 (21 November 2018). The main purpose of changes to the versions 1.0 and 2.0 of the Statistical Analysis Plan was to accommodate additional patients treated with edoxaban and patients in Japan, and to align the SAP with the last version of the protocol (i.e., amendment 5 and 6).

The main change to the SAP (as in the protocol) regards the definition of efficacy evaluable patient population to include requirement of a minimum anti-fXa activity level for edoxaban as follows:

The Efficacy Population will include all patients in the Safety Population who meet all of the following criteria:

- · Are determined by the EAC to meet the clinical bleeding inclusion criteria.
- Have a baseline anti-fXa level
- Baseline anti-fXa level of at least 75 ng/mL for apixaban and rivaroxaban, 40 ng/mL for edoxaban, or 0.25 IU/mL for patients receiving enoxaparin.

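### The mortality model labelled as reversal omits baseline anti-fXa, so a low nadir partly stands for a low starting level

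*SAP*

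**What the plan says.** The mortality model in SAP 5.16.3 "will be analyzed (in the safety population), using a logistic regression model, with Age included as a covariate". The Reduced Model contains a cubic spline in age and nothing else. The Full Model adds "an indicator variable for anti-fXa at on-treatment Nadir < threshold (where the threshold is 30 ng/mL for the DOACs, and 0.10 IU/mL for Enoxaparin"). The two are compared by a likelihood-ratio test at 0.05.

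The on-treatment nadir is the lower of the end-of-bolus and end-of-infusion values (SAP 4.3). It is therefore a level reached, not a change. If both samples are missing, SAP 5.5.1 carries the baseline value forward as the nadir.

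The population has no baseline requirement: "The Safety Population will consist of all patients treated with any amount of andexanet" (SAP 5.2.1). The Efficacy Population does have one: "Baseline anti-fXa level of at least 75 ng/mL for apixaban and rivaroxaban, 40 ng/mL for edoxaban, and 0.25 IU/mL for patients receiving enoxaparin" (SAP 5.2.2).

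The hemostasis models in SAP 5.14 use a different set: "Efficacy, excluding patients with Non-Evaluable Hemostatic Efficacy due to Admin reason".

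SAP 5.17.2 lists the mortality analysis as the "correlation between reversal of anti-fXa activity with mortality".

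Low baselines are expected. Protocol 3.4.2 explains that "it is not possible to use anti-fXa activity as a marker of anticoagulation for purposes of enrollment into the study", and Protocol 11.6 estimates that "approximately 30% of the andexanet-treated patients will have pre-andexanet anti-fXa activity of < 75 ng/mL", with corresponding cut-offs for edoxaban and enoxaparin.

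**The concern.** The indicator depends on two things: how far andexanet lowered the level, and where the level started. Only the first is reversal. With baseline left out, the odds ratio for the indicator carries both.

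For DOAC patients this happens in two ways. A patient who starts below 30 ng/mL is coded as below threshold whatever andexanet does, including by carry-forward when both post-dose samples are missing. Protocol 1.4.4 itself describes 30 ng/mL as an estimated non-effective level of inhibition, so such a patient had little to reverse. Above 30, the higher the baseline, the larger the percentage fall needed to get under the line.

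If the risk of death varies with baseline level, or with anything that tracks it, the test can reject when reversal has no effect on survival. The study has a single arm, and the SAP supports FDA and EMA submissions (SAP 1.0). A significant odds ratio from an analysis described as reversal against mortality could be read as evidence that reversal changes survival.

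**Working it through.** **What the plan gives.** There is no expected odds ratio, event rate or power for the mortality model, so no plan figure for it can be reproduced. The relevant figures are 477 patients (SAP 1.0) and about 30% below the evaluability cut-off: 0.30 × 477 ≈ 143 patients who are outside the Efficacy Population on baseline level but inside the mortality model. The share below 30 ng/mL is not given.

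**Reduction needed to reach a nadir below 30 ng/mL.** It is 1 − 30/baseline:

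| Baseline (ng/mL) | Reduction needed |
|---|---|
| 30 or lower | none, or any fall at all |
| 75 | 60% |
| 150 | 80% |
| 300 | 90% |
| 600 | 95% |

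With an assumed median reduction of 92%, half the patients reach the indicator when baseline = 30/0.08 = 375 ng/mL. The indicator therefore depends on baseline across the whole range, not only below 30.

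**Direction, by hand.** Suppose 10% start below 30, half of the rest are brought below 30, and reversal has no effect. The below-threshold group is then 0.10 + 0.90 × 0.5 = 0.55 of patients.
- Deaths 10% in those already low, 18% in the rest: (0.10 × 0.10 + 0.45 × 0.18)/0.55 = 16.5%, against 18%; odds ratio 0.90.
- Deaths 22% in those already low, 15% in the rest: (0.10 × 0.22 + 0.45 × 0.15)/0.55 = 16.3%, against 15%; odds ratio 1.10.

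The sign follows an assumption that the documents do not supply.

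**Size, by simulation with no effect of reversal.** Assumptions, none given by the plan for this model except the 477 and the 30%: lognormal baseline with 30% below 75 ng/mL, capped at 950; median reduction 92%; 16% mortality; mortality odds multiplied by 1.15 or 1.3 per doubling of baseline; 1-df likelihood-ratio test at 0.05.

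| Share below 30 ng/mL | Odds per doubling | Rejection as written |
|---|---|---|
| 5% | 1.15 | about 10% |
| 5% | 1.3 | about 23% |
| 10% | 1.15 | 16-19% |
| 10% | 1.3 | 44-49% |
| either | 1.0 | about 5% |

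Apparent odds ratios run from about 0.8 to about 0.6. With log baseline in both models, rejection is about 3-6%.

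**Which part of the mechanism matters.** At 10% below 30 and 1.15 per doubling:

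| Version | Rejection |
|---|---|
| As written | 19% |
| Excluding baseline below 30 | 14% |
| Baseline 75 or above only | 11% |
| All patients, log baseline added | about 6% |

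A second set of runs used a different parameterisation: odds ratio 1.22 or 1.49 per SD of log baseline, 7-12% of patients below 30, and median residual activity 8% or 25%. At 1.22 the test as written rejected in 14-18% of trials, baseline 75 or above in 7-9%, and the adjusted model in 5-6%. At 1.49 the figures were 42-58%, 14-27% and 5-6%.

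**Enoxaparin.** SAP 5.5.1 replaces values below 0.10 IU/mL with 0.10. A value of 0.05 becomes 0.10, and 0.10 < 0.10 is false. Read literally, no enoxaparin patient can meet the indicator.

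**The case against.** The best defence is that the achieved level is the intended exposure. SAP 5.14 argues, for hemostasis, that the level in the first hours matters more than the decrease, and the operative sentence in SAP 5.16.3 speaks of anti-fXa rather than reversal; that word appears only in the list of changes. The model supports no primary or secondary endpoint, and SAP 5.7 treats even secondary analyses as exploratory. All this lowers the stakes, and the difference in wording is not itself an error. It does not remove the problem: a level-based exposure is still confounded by baseline, and no other planned analysis adjusts mortality for it. The sensitivity analyses by baseline level (SAP 5.13.1.1) cover only the two primary efficacy endpoints. The confounder analyses in SAP 5.15.1.11 concern hemostasis. The one mortality sensitivity analysis changes only the death window.

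Three stronger readings are tempting and are not supported.
- A reader might blame the Safety Population and the patients already below 30. Removing those patients cuts rejection only from 19% to 14%, and bias remains at baseline 75 or above. The larger cause is the omitted baseline. The hemostasis models omit it too, although nobody in them starts below the threshold.
- A reader might infer a spurious survival benefit. SAP 5.3 links concentration to bleeding, not to death among patients already bleeding, so the direction is open.
- A reader might assume 20% below 30 and obtain rejection rates of 42-85%. With 30% below 75, a lognormal then needs a median of 341 ng/mL and puts 36% of patients above the 950 cap. Protocol 3.4.3 implies an apixaban peak near 37/0.25 = 148 ng/mL. The 10% scenario has a median of 141.

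**Conclusion.** The point stands as an omitted-covariate problem in a supportive analysis. SAP 5.16.3 cannot separate reversal from starting level in DOAC patients, and its test can reject without any effect of reversal if mortality depends on baseline. The rejection rate of about 10-49%, with odds ratios of about 0.8-0.6, holds only under the listed assumptions and for mortality that rises with baseline. If low-baseline patients die more often, the bias runs against reversal. If there is no such relation, every version is near 5%. The mechanism does not extend to enoxaparin as the rules are written, because the floor in SAP 5.5.1 makes the indicator unreachable; that is a separate inconsistency to settle. Neither primary endpoint is affected.

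**What to change.** In SAP 5.16.3:
1. Add log baseline anti-fXa to both the Reduced and the Full Model, fitted to the same patients. Fit it in DOAC patients, or use inhibitor-specific baseline terms, so that ng/mL and IU/mL are not pooled. A DOAC-only log level follows the SAP's own Model 3 in 5.14.
2. Add, as a sensitivity analysis, a run in patients who meet the baseline evaluability threshold. Restriction should not replace adjustment: it gives up about 30% of patients and leaves some bias.
3. Tabulate, by inhibitor, how many patients counted as below threshold were already below it before dosing.
4. Reconcile the enoxaparin indicator (<0.10) with the replacement of values <0.10 by 0.10 in SAP 5.5.1, and apply the same rule in SAP 5.14.

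The cost is SAP wording, one extra model run and a slightly wider confidence interval. Patients with no baseline value drop out of the adjusted fit and should be counted. No new data are needed: Listing 16.2.6.1 already covers anti-fXa levels by patient for the Safety Population.

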5.5. Handling of Dropouts and Missing Values

5.5.1. Anti-fXa Activity

For patients treated with apixaban, rivaroxaban, and edoxaban, anti-fXa values greater than 950 ng/mL the anti-fXa value will be replaced with 950. If the anti-fXa value is < 4.0 ng/mL then the value will be replaced with 4.0. For enoxaparin treated patients, anti-fXa values identified as < 0.10 IU/mL will be replaced with 0.10.

If the baseline anti-fXa activity is missing, the patient will be excluded from the efficacy analysis population. For post baseline assessments, if both the EOB and EOI assessments are missing, the maximum change will be replaced with zero (i.e., no change from baseline) and the Nadir will be replaced with the baseline value using the Baseline Observation Carried Forward principle (BOCF principle). If only one post-baseline sample is missing, the available sample (either EOB or EOI) will be used for the imputation (Last Observation Carried Forward [LOCF]).

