5.5.4. Ambiguous Values

In the case where a variable is recorded as "> x", " \geq x", " \leq x", " \leq x", then for analysis purposes a value of x will be taken. Where a range of values is quoted the midpoint of the range

will be taken. In the case where a patient records more than one score for any particular measure, the worst of the recorded scores will be taken for analysis purposes. In all cases, sites will be queried first to determine whether a more precise value is available.

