 the value will be taken as LLOQ threshold value.
- For plasma concentrations that are higher than the upper level of quantification (ULOQ) then the value will be taken as ULOQ threshold value.

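### SAP 5.16.3 and 5.14 (Models 1 and 4): once 5.5.1 has set low enoxaparin values to 0.10 IU/mL, no enoxaparin patient can fall strictly below 0.10; the 30-day mortality model also leads with death at any time

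*SAP*

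**What the plan says.** **Low values.** SAP 4.3 defines the on-treatment nadir as the smaller of the end-of-bolus and end-of-infusion values. For enoxaparin, SAP 5.5.1 says that "anti-fXa values identified as < 0.10 IU/mL will be replaced with 0.10". For the direct inhibitors it says: "If the anti-fXa value is < 4.0 ng/mL then the value will be replaced with 4.0". If both on-treatment samples are missing, baseline is carried forward. SAP 5.5.4 handles results recorded with an inequality sign in the same way ("then for analysis purposes a value of x will be taken"). SAP 5.9 does so for plasma concentrations below the quantification limit ("the value will be taken as LLOQ threshold value").

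**Indicator.** SAP 5.14 states that "the threshold for the Enoxaparin patients in the analysis will be the lower limit of detection (0.10 IU/mL". The mortality Full Model in SAP 5.16.3 adds to age an "indicator variable for anti-fXa at on-treatment Nadir < threshold (where the threshold is 30 ng/mL for the DOACs, and 0.10 IU/mL for Enoxaparin". Models 1 and 4 in SAP 5.14 use the same strict indicator in populations that include enoxaparin. Models 2 and 3 do not ("Same as (1) except exclude Enoxaparin patients also").

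**Outcome.** For the mortality model, SAP 5.16.3 says that "30-day mortality will define Death as Death at any time (including deaths recorded after Day 30". Death during the 30-day follow-up is the sensitivity analysis. Protocol 2.4 and SAP 2.4 give 30-day all-cause mortality as the objective. The death proportion and the Kaplan-Meier analysis, also in SAP 5.16.3, are tied to Day 30.

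**The concern.** The enoxaparin threshold was set at the detection limit so that patients with undetectable activity would count as having reached a low level. The replacement rule moves exactly those patients onto the threshold, and the strict inequality then excludes them. The coding becomes asymmetric by drug: DOAC patients can be coded 1 and enoxaparin patients cannot. The pooled comparison is then partly DOAC against enoxaparin. SAP 5.14 has enoxaparin-free models to set beside Model 1, but Model 4 and the mortality model have no such companion.

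The outcome raises a separate and smaller issue. A logistic model does not censor, so a death after Day 30 enters only if the patient was still being observed. Such observation is uneven. The final visit may fall anywhere from Day 30 to Day 37 (Protocol Appendix A, footnote 12). Follow-up was 45 days before Amendment 2 (SAP 5.17.1.2), and some patients enrolled under Amendment 1 (SAP 5.17.1). The report would carry two different outcomes under a 30-day label.

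**Working it through.** The plan gives no figure for either point, so there is none to reproduce. The first step is pure logic. The later steps only indicate size and rest on assumed inputs.

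**1. Can the enoxaparin indicator equal 1?**
- After SAP 5.5.1, every enoxaparin value is ≥ 0.10, so min(end of bolus, end of infusion) ≥ 0.10.
- If both samples are missing, the nadir is the baseline value, which is also ≥ 0.10.
- The condition nadir < 0.10 is therefore false for every enoxaparin patient.
- For DOACs the floor is 4.0 ng/mL and the threshold 30 ng/mL. A value below 4.0 becomes 4.0 and still meets < 30, so no code changes.

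**2. How many patients could be miscoded?** N = 477 (SAP 1.0). The protocol aims to keep indirect inhibitors at or below 20% (Protocol 3.1). Assume an enoxaparin share s of 5–20% (24–95 patients), with a fraction u of 25–50% truly below 0.10. Miscoded = 477 × s × u:
- s = 5%: 6 (u = 25%) to 12 (u = 50%)
- s = 20%: 24 (u = 25%) to 48 (u = 50%)

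**3. What could this do to the pooled odds ratio?** Assume no true effect, 70% of DOAC patients below 30 ng/mL, DOAC mortality 15%, u = 50%, and no age adjustment. As written, the coded-0 group has mortality [(1−s)(0.30)(0.15) + s·mE] / [(1−s)(0.30) + s], where mE is enoxaparin mortality; the coded-1 group has 15%. Under the intended coding, s × u moves to coded 1.

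Example, s = 20%, mE = 10%, as written: coded 0 = (0.24 × 0.15 + 0.20 × 0.10)/0.44 = 12.7%. OR = (0.15/0.85)/(0.127/0.873) = 1.21.

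| Share s | mE | OR as written | OR intended |
|---|---|---|---|
| 5% | 10% | 1.06 | 1.02 |
| 5% | 25% | 0.89 | 0.97 |
| 20% | 10% | 1.21 | 1.06 |
| 20% | 25% | 0.73 | 0.90 |

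If mE = 15%, both codings give 1.00. With a true OR of 0.70, 18% mortality when not low and u = 50%, the coding as written gives 0.72 (s = 5%) to 0.75 (s = 20%).

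For scale, with 70% coded 1 and 15% mortality, SE(log OR) = √[1/(333.9 × 0.15 × 0.85) + 1/(143.1 × 0.15 × 0.85)] = 0.280. The 95% range around OR 1 is exp(±1.96 × 0.280) = 0.58 to 1.73.

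**4. How much could late deaths matter?** Assume 72 of 477 (15%) die by Day 30.
- One to ten late deaths add 1/477 = 0.2 to 10/477 = 2.1 percentage points, or 1/72 = 1% to 10/72 = 14% of the Day-30 events.
- The average daily hazard to Day 30 is −ln(0.85)/30 = 0.00542. If the later hazard is 10–50% of that, a Day-30 survivor has a 0.4–1.9% chance of a recorded death over 7 more days (to Day 37) and 0.8–4.0% over 15 more days (to Day 45). A patient last seen alive on Day 30 has none.

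**The case against.** **Intent and order of derivation.** SAP 5.14 calls 0.10 the detection limit, so the intent is plainly undetectable activity, and a programmer could take that from the raw result. The SAP does not say whether the indicator precedes or follows replacement. The SAP 5.9 rule concerns plasma concentrations, so it supports the point only by analogy. All of this is fair. But SAP 5.5.1 covers enoxaparin anti-fXa directly and gives no exception, and SAP 5.5.4 points the same way. Elsewhere the SAP does place low values below the limit: TFPI under 0.2 becomes 0.1, and anti-IIa under 0.04 becomes 0.02. Here it does not.

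**Disclosure of the outcome.** The any-time definition is stated openly and the Day-30 fit is already planned, so both results will exist. The objective is answered separately by the Day-30 proportion and the Kaplan-Meier curve. The 45-day follow-up concerns only patients enrolled before Amendment 2, whose number is not given. This stands, and it reduces the second point to which result leads and what it is called.

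**Size.** The shifts lie within sampling error, and some DOAC-against-enoxaparin contrast remains under the intended coding (1.06 and 0.90 at a 20% share). This also stands: the fix corrects the coding but does not remove every drug difference.

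**Stronger readings.** A reader might infer from SAP 5.16 that a separate enoxaparin mortality model is planned and cannot be estimated. That section asks for results by inhibitor only unless otherwise indicated, and SAP 5.14 explains that the dichotomy exists to allow pooling. If such a stratum were fitted, the indicator would be constant, but the plan does not clearly require it. A reader might also object that the change list in SAP 5.17.2 speaks of reversal while the model uses an achieved level. That list summarises changes, and the operative text in SAP 5.16.3 never calls the indicator reversal, so no inconsistency follows.

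**Conclusion.** The enoxaparin rule is wrong as written. Followed literally, it codes every enoxaparin patient as not low in the mortality model and in SAP 5.14 Models 1 and 4. This depends only on applying the SAP 5.5.1 replacement before deriving the indicator, which is how the SAP reads. DOAC coding and Models 2 and 3 are unaffected.

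The outcome point holds in a smaller form: a model labelled 30-day mortality leads with a definition that depends on how long each patient was observed, while the rest of the section and the objective use Day 30.

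Both effects are probably small and of unknown direction. The enoxaparin share, the fraction below the limit, the mortality rates and the number of late deaths are assumptions throughout. No primary objective depends on these models, and the documents do not support a claim that the trial's main conclusions are at risk. The corrections are still worth making before the analysis is run, because SAP 5.17.2 presents both relationship analyses as pre-specified.

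**What to change.** 1. In SAP 5.16.3 and in SAP 5.14 Models 1 and 4, define the enoxaparin indicator as nadir ≤ 0.10 IU/mL, or derive it from the raw laboratory result before replacement, and state which. The cost is one operator or one derivation step. With ≤ 0.10, a patient measured at exactly 0.10 joins those below the limit; the raw result avoids this.

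2. In SAP 5.16.3, make death on or before Day 30 the main outcome and keep the any-time definition as the sensitivity analysis. Both fits are already planned, so the cost is wording, and a few late deaths leave the main model. At the least, rename the any-time outcome as all recorded deaths.

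No other change to the model is needed for these points.
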